	
prior to study entry;
 
 3. Use of surfactant prior to study entry and need for intratracheal administration of any other treatment (e.g. nitric oxide); 4. Known genetic or chromosomal disorders, major congenital anomalies (congenital heart diseases, myelomeningocele, etc); 5. Mothers with prolonged premature rupture of the membranes (>21 days duration) which could cause complications (in particular severe pulmonary hypoplasia due to oligohydramnios); 6. Presence of air leaks if identified and known prior to study entry; 7. Evidence of severe birth asphyxia (e.g. continued need for resuscitation at 10 minutes after birth, altered neurological state or neonatal encephalopathy); 8. Neonatal seizures prior to study entry; 9. Any condition that, in the opinion of the Investigator, would place the neonate at undue risk; 10. Participation in another clinical trial of any medicinal product, placebo, experimental medical device or biological substance conducted under the provisions of a protocol on the same therapeutic target; the participation in studies involving diagnostic devices or studies with treatments for different conditions than lung and respiratory function impairments may be permitted following an agreement with the sponsor. Non-interventional observational studies are allowed.

Most relevant allowed concomitant treatments
	
Any concomitant medication required for the normal care of preterm neonates will be permitted during the study.
 
The use of sedative/analgesic medication, as well as the use of atropine, before/during surfactant administration, will be at investigator's discretion, according to each neonatal intensive care unit (NICU) standard practice. If premedication is used, the Investigator should define a protocol (with specification of drugs and dosages) before starting enrollment, which allows for a step-by-step management of pain and sedation for the endotracheal administration of surfactant. Each neonate will be managed according to the pre-defined protocol, and decision on which step of the protocol to apply should be based on neonate's needs. The same step-by-step protocol should be applied to both treatment arms. The protocol will be provided to the Sponsor.
 
If caffeine is administered, it should be used in both treatment arms.

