	
 • Weight, OFC and length at discharge home or 40 weeks PMA will be summarized by treatment group by descriptive statistics. • Percentage of neonates needing invasive or non-invasive respiratory support at discharge home or 40 weeks PMA will be summarized by treatment group by frequency distribution • Neonates needing respiratory medications at discharge home or 40 weeks PMA will be summarized by treatment group by frequency distribution • Bayley Scales of Infant Development (BSID) (cognitive and language scores) will be summarized using descriptive statistics by treatment group and BSID version (III or IV). • Vital signs and all other variables collected through the questionnaire (i.e., anthropometric measures, cerebral palsy, seizures, feeding method, functional disability and respiratory morbidity) will be summarized by treatment group by frequency distribution or descriptive statistics as appropriate.
Statistical methods	Efficacy variables 
 • Percentage of neonates needing invasive mechanical ventilation in the first 72 hours of life, in the first 28 days PNA and within 36 weeks PMA will be compared between groups using the Cochran-Mantel-Haenszel (CMH) test adjusted for gestational age group. The CMH adjusted difference with its 95% confidence interval (CI) will be presented. Additional analysis will be performed to explore the impact of use of sedation and/or analgesia. • Duration of invasive mechanical ventilation in the first 72 hours of life, in the first 28 days PNA and within 36 weeks PMA will be compared between treatment groups by using the Mann-Whitney U-test. • Percentage of neonates needing any intubation procedure, outside the initial surfactant administration period, in the first 72 hours, in the first 28 days PNA and within 36 weeks PMA will be compared between treatment as need for invasive mechanical ventilation. • SpO₂ will be analysed using a linear mixed model for repeated measures (MMRM) including treatment, time point, treatment by time point interaction, and gestational age group as fixed effects and pre-procedure SpO₂ as covariate. The adjusted means in each treatment group, the adjusted mean difference between treatments and their 95% CIs at each time point and averaged over the first 120 hours post treatment will be estimated by the model. Time profile plot of mean SpO₂ in the first 120

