3. STUDY DESIGN

This is an open-label, multicenter, randomized and controlled study. Approximately 25 investigational sites will be involved in US. Neonates will be evaluated according to the selection criteria and then randomized to surfactant treatment via LISA or standard administration procedure ([Table 1](#)). The enrollment will be staggered: the gestational age will be restricted to 27⁺⁰ weeks up to 28⁺⁶ completed weeks until safety evaluation by ISMB is performed for the first 15 neonates. Provided no safety concerns are raised, the enrollment will then be extended to the whole population (i.e. 25⁺⁰ weeks up to 28⁺⁶ completed weeks).

[figure not shown]
Enrolled neonates will be evaluated:

- until discharge,
- until 40 weeks PMA (if still in hospital),
- if discharge occurs before 36 weeks, the last evaluation will be at 36 weeks PMA.

This period represents the main phase of the trial.

Their final assessment of development will be at 24-month corrected age as a separate stand-alone visit. This 24-month clinical assessment will be analyzed and evaluated separately from the initial part of the study and will be object of an addendum to the initial core clinical study report.

Table 1: TIMETABLE

End of the trial

The end of the trial will correspond to the last evaluation of the last neonate from the recruiting site or from the continuing care site in case the treated baby was transferred from the original recruiting site. The last evaluation could be:

- the date of the assessment for BPD diagnosis (i.e. 36 weeks PMA) if the patient is discharged home before 36 weeks PMA,
- discharge home (if discharged between 36 weeks and 40 weeks PMA), or
- 40 weeks PMA (if still in hospital).

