6.5 Treatment allocation

A balanced block randomization scheme stratified by investigational site and gestational age group (i.e. from 25⁺⁰ to 26⁺⁶ weeks and from 27⁺⁰ to 28⁺⁶ weeks) will be prepared via a computerized system. Once the neonate’s eligibility to take part in the study is confirmed, neonates will be centrally assigned to one of the two treatment arms (LISA/Poractant alfa or ETT/Poractant alfa) through an IRT system (Interactive Response Technology, combination of voice and web response system and also referred as IVRS/IWRS). Enrollment will be staggered: the gestational age will be restricted to 27⁺⁰ to 28⁺⁶ weeks for at least the first 15 randomized neonates. After ISMB evaluation of safety data from the first 15 neonates, provided no safety concerns are raised, the enrolment will be extended to the whole population (25⁺⁰ to 26⁺⁶ weeks and from 27⁺⁰ to 28⁺⁶ weeks).

The IRT will allocate the subject to a certain treatment group using a list-based randomization algorithm and assign the unique screening number of eight digits: the country will be the first three digits (according to ISO 3166 Numeric Country Code), the investigational site number will be the second two digits and the following three digits will be the progressive numbering of the subject within each site (e.g. for the first USA site the screening numbers will be 84001001, 84001002 etc.). The IRT will also generate a confirmation after every IRT transaction is performed.

The Investigator will call the IRT on admission to receive the subject screening number and randomize the subject and obtain the medication (Poractant alfa) kit numbers. Detailed instructions for use of IRT will be provided to the site.

In the LISA group, the relevant catheter provided by the Sponsor (CHF 6440) will be dispensed and used for administration. In the control group, the endotracheal tubes available at the investigational sites for clinical practice will be used for administration.

The LISA catheter (CHF 6440) will be dispensed by the IRT system.

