12. STATISTICAL METHODS

12.1. Sample Size

No primary efficacy endpoint was defined in this study since the main objective is to describe the overall safety and efficacy profile of administering poractant alfa with two different

procedures: LISA technique or conventional administration with endotracheal tubes and brief invasive ventilation. A total of 150 neonates will be randomized in the study with a ratio 2:1 to LISA arm (i.e. 100) and conventional administration arm (i.e. 50).

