12.3.4. Efficacy variables

Need for mechanical ventilation/intubation

- Percentage of neonates needing invasive mechanical ventilation in the first 72 hours of life, in the first 28 days PNA and within 36 weeks PMA will be compared between group using the Cochran-Mantel-Haenszel (CMH) test adjusted for gestational age group. The CMH adjusted difference with its 95% CI will be presented. Additional analysis will be performed to explore the impact of use of sedation and/or analgesia.
- Percentage of neonates needing any intubation procedure, outside the initial surfactant administration period, in the first 72 hours of life, 28 days PNA and within 36 weeks PMA will be compared between treatments as need for IMV.

SpO₂

- SpO₂ will be analyzed using a linear mixed model for repeated measures (MMRM) including treatment, time point, treatment by time point interaction, and gestational age group as fixed effects and pre-procedure SpO₂ as covariate. The adjusted means in each treatment group, the adjusted mean difference between treatments and their 95% CIs at each time point and averaged over the first 120 hours post-treatment will be estimated by the model. Time profile plot of mean SpO₂ in the first 120 hours post-administration will be presented by treatment group.
- SpO₂ will be summarized by treatments on neonates still receiving respiratory support at 28±2 PNA and 36 weeks PMA by means of descriptive statistics.

FiO₂

- FiO₂ will be analyzed using a linear MMRM including treatment, time point, treatment by time point interaction, and gestational age group as fixed effects and pre-procedure FiO₂ as covariate. The adjusted means in each treatment group, the adjusted mean difference between treatments and their 95% confidence intervals (CIs) at each time point and averaged over the first 120 hours post-treatment will be estimated by the model. Time profile plot of mean FiO₂ in the 120 hours post-treatment will be presented by treatment group.
- FiO₂ will be summarized by treatments on neonates still receiving respiratory support at 28±2 PNA and 36 weeks PMA by means of descriptive statistics.

SpO₂/FiO₂ ratio

- SpO₂/FiO₂ will be analyzed using a linear MMRM including treatment, time point, treatment by time point interaction, and gestational age group as fixed

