- Number of maneuvers discontinued due to neonate's severe destabilization will be summarized by treatment group by means of descriptive statistics.
- Duration of surfactant administration (min) and overall procedure for surfactant administration will be compared between treatment groups by using the Mann-Whitney U- test.

Mortality and BPD

- Death/BPD incidence at 36 weeks PMA will be compared by treatment by means of CMH test, adjusting for GA group and related 95% confidence interval will be provided.

- The incidence of BPD at 36 weeks PMA will be compared by treatment as for Death/BPD incidence.
- The mortality at 36 weeks PMA and at Day 28 will be compared by treatment as for Death/BPD incidence.
- Oxygen use at Day 28 (alone and / or during any kind of MV) will be compared by treatment as for Death/BPD incidence.

Other safety variables

- Feeding and hearing status at discharge or 40 weeks PMA (whichever comes first) will be summarized by treatment group by frequency distributions.
- Weight, OFC and length at discharge home or 40 weeks PMA will be summarized by treatment group by descriptive statistics.
- Neonates needing invasive or non-invasive respiratory support at discharge home or 40 weeks PMA will be summarized by treatment group by frequency distribution
- Neonates needing respiratory medications at discharge home or 40 weeks PMA will be summarized by treatment group by frequency distribution

Health status questionnaire at 24 months (± 3 months) corrected age

(This stand-alone assessment will be analyzed and reported separately from the main phase)

- Bayley Scales of Infant Development (cognitive and language scores) will be summarized using descriptive statistics by treatment group and BSID version (III or IV).
- Vital signs and all other variables collected through the questionnaire (i.e., anthropometric measures, cerebral palsy, seizures, feeding method, functional disability and respiratory morbidity) will be summarized by treatment group by frequency distribution or descriptive statistics, as appropriate.

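### Site is a randomisation stratum but is missing from the three oxygenation MMRMs; where sites differ, their standard errors and intervals are mildly conservative, and a random site intercept would correct this cheaply

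*Protocol*

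**What the plan says.** **Allocation.** Protocol section 6.5 specifies "A balanced block randomization scheme stratified by investigational site and gestational age group", with two GA groups split at 27 weeks. Section 3 states "Approximately 25 investigational sites will be involved in US", and section 12.1 states "A total of 150 neonates will be randomized in the study with a ratio 2:1" (100 LISA, 50 conventional).

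**Continuous oxygenation outcomes.** The outline (Statistical methods, Efficacy variables) and section 12.3.4 both write out the model terms for SpO₂: "including treatment, time point, treatment by time point interaction, and gestational age group as fixed effects". The list closes with "gestational age group as fixed effects and pre-procedure SpO₂ as covariate". Section 12.3.4 repeats this structure for FiO₂ and SpO₂/FiO₂; the outline says that they are analysed in the same way as SpO₂. Estimates with 95% confidence intervals are promised at each time point and averaged over the first 120 hours. No random effect is named, and site does not appear.

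**Other comparisons.** The binary efficacy outcomes use a "Cochran-Mantel-Haenszel (CMH) test adjusted for gestational age group". For safety, "Death/BPD incidence at 36 weeks PMA will be compared by treatment by means of CMH test, adjusting for GA group", and BPD, mortality and oxygen use at Day 28 follow the same method. Durations use the Mann-Whitney test and additional surfactant doses use Fisher's exact test, both unstratified.

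**Status of the study.** Section 12.1 says that the aim is descriptive and that there is no primary efficacy endpoint. No effect size, power or target precision is given. Section 12.3 refers to a separate SAP, which is not at hand.

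**The concern.** An analysis normally reflects the factors used to restrict the randomisation. Balancing the arms within sites keeps part of the between-site variation out of the difference between arms. If the model has no site term, that variation still enters the residual variance and hence the standard error. The reported interval is then wider than the true sampling error warrants, and the nominal 5% test rejects less often than 5%.

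The protocol gives some reason to expect site differences. Sedation, analgesia and atropine are used "according to each neonatal intensive care unit (NICU) standard practice", under a premedication protocol set by each investigator. Several modes of non-invasive support are allowed. Control neonates may be extubated at once or ventilated for up to an hour.

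The point carries some weight because, with no primary endpoint and only 50 controls, the estimates and their intervals are the main product of these models.

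**Working it through.** **Inputs from the protocol:** 150 neonates, 2:1 allocation, about 25 sites, 2 GA groups. There is no stated precision or power to reproduce.

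**Stratum size.** 150 / 25 = 6 neonates per site. 25 × 2 = 50 strata, and 150 / 50 = 3 neonates per stratum. Many blocks will be incomplete, so balance within site is only partly achieved.

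**Assumptions not in the protocol:** site ICC from 0 to 0.20, blocks of 3 or 6, a 50/50 GA split, equal or skewed site sizes, one measurement per neonate, no baseline covariate. In the random-effect analysis the ICC was treated as known.

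**Analytic guide.** With full balance within sites, the ratio of the standard error (SE) without site to the SE with site is 1/√(1 − ICC): 1.026 at ICC 0.05, 1.054 at 0.10 and 1.118 at 0.20. Incomplete blocks should give somewhat less.

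**Simulation, continuous outcome.** 95% half-widths in SD units, GA-only model / model with random site effect:

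| ICC | Equal sites, block 3 | Equal, block 6 | Skewed, block 3 | Skewed, block 6 | Excess width |
|---|---|---|---|---|---|
| 0 | 0.3422 / 0.3430 | 0.3432 / 0.3436 | 0.3422 / 0.3428 | 0.3418 / 0.3431 | about 0 |
| 0.05 | 0.3418 / 0.3358 | 0.3421 / 0.3378 | 0.3420 / 0.3354 | 0.3423 / 0.3365 | 1.3–2.0% |
| 0.10 | 0.3424 / 0.3278 | 0.3430 / 0.3308 | 0.3412 / 0.3274 | 0.3415 / 0.3290 | 3.7–4.5% |
| 0.20 | 0.3413 / 0.3103 | 0.3410 / 0.3146 | 0.3395 / 0.3099 | 0.3397 / 0.3124 | 8.4–10.0% |

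Coverage of the GA-only interval was 0.947–0.952 at ICC 0 and 0.960–0.967 at ICC 0.20. The error is therefore on the conservative side.

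**Where the difference arises.** At ICC 0.10 (equal sites, block 3) the true sampling SE was 0.1688 without site and 0.1676 with it, almost the same. The SE that the model reports was 0.1732 without site and 0.1659 with it. The estimate itself is barely less precise; the reported SE is too large.

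**Second simulation.** 4,000 trials per setting, unequal sites, 35% of neonates in the lower GA group, site intercept estimated by REML. The GA-only SE was 2–4% too large at ICC 0.10 and 7–8% at 0.20, where type I error was 3.4–3.8%.

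**Site as a fixed effect** is not a good alternative. At ICC 0 its half-width in the equal-site, block-6 layout was 0.3597 against 0.3432 for GA only, that is 4.8% wider.

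**Binary outcomes.** The Mantel-Haenszel risk difference was stratified by GA alone or by GA × site. With GA × site, about 135–136 of 150 neonates stay informative, so 14–15 (9–10%) are lost in one-arm strata. Reported SEs, GA × site against GA alone:

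| Latent ICC | Equal sites | Skewed sites |
|---|---|---|
| 0 | 0.0849 v 0.0804 | 0.0844 v 0.0802 |
| about 0.10 | 0.0825 v 0.0810 | 0.0821 v 0.0806 |
| about 0.20 | 0.0800 v 0.0815 | 0.0795 v 0.0813 |

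Stratifying by site and GA thus widens the interval up to a latent ICC of about 0.10 and narrows it by only about 2% at 0.20.

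**The case against.** The strongest reply is that the protocol lists fixed effects of a mixed model and says nothing of random effects or covariance structure. A random site intercept is not excluded, and the SAP may contain one. That is fair as far as it goes. But the protocol writes out its model terms in two places and takes up one of its two stratification factors; nothing in it brings site in, and an SAP that followed this wording would leave site out.

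The second reply is that the loss may be negligible. It needs a between-site variance that the protocol does not give. The planned models adjust for the pre-procedure value, which would absorb any site difference already present at baseline. All sites work to one SpO₂ target of 88–95% and to common intubation criteria in the first 72 hours. None of this was simulated. This stands, and it is why the size is given as a range that starts at zero.

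A reader might infer more: that every planned test loses precision for want of site, or that the trial loses power. The documents do not support either. No gain was shown for the Mann-Whitney or Fisher comparisons, and for the CMH tests the obvious change usually does harm. A power loss can be computed only from an effect size that the protocol never states, in a study that it calls explorative.

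**Conclusion.** The mismatch is real but minor. Site restricts the randomisation and is absent from the three oxygenation MMRMs, with no reason given. If sites differ, the reported standard errors and 95% intervals for SpO₂, FiO₂ and SpO₂/FiO₂ are mildly conservative: about 1–2% too wide at an assumed ICC of 0.05, about 4% at 0.10 and roughly 8–10% at 0.20. If sites do not differ, nothing is lost.

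These figures rest on the assumed ICCs and on a single measurement per neonate without the baseline covariate, so they indicate scale and do not predict what the full MMRM would show. There is no bias and no inflation of type I error, and it would be wrong to read the omission as a threat to validity. The GA-only CMH tests are a defensible choice given strata of about three neonates.

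**What to change.** In section 12.3.4, and in the matching outline text, add investigational site as a random intercept to the MMRMs for SpO₂, FiO₂ and SpO₂/FiO₂. State in advance that the model without site will be used if the fit does not converge. Do not enter site as about 25 fixed effects.

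Leave the GA-adjusted CMH tests unchanged, and do not stratify them by site and GA.

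The cost is a change of wording in the protocol (and in the SAP, if it follows the protocol) and one extra variance parameter per model. Site is already recorded for every neonate, so no new data are needed and trial conduct does not change.

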1. INTRODUCTION

1.1 Background Information and Study Rationale

Respiratory distress syndrome (RDS) is the most common respiratory disease of premature neonates and its incidence is directly proportional to the degree of prematurity. The National Institute of Child Health and Human Development (NICHD) Neonatal Research Network showed a 93% incidence of RDS in a cohort of 9575 extreme premature neonates with gestational age (GA) of 28 weeks or below, born between 2003 and 2007 [1]. In fact, despite a constant improvement of neonatal care, RDS still represents one of the major causes of mortality in preterm neonates, as confirmed in a recent US review (64 deaths per 1000 live births) [2].

The clinical features of RDS start appearing soon after birth. RDS is characterized by tachypnea (rapid breathing), expiratory grunting, subcostal and intercostal retractions, cyanosis, nasal flaring, apnea and/or hypothermia in extremely immature neonates. In the pre-surfactant era, the disease led rapidly to progressive respiratory failure in the first 2-3 days of life [3] and, in the most severe cases, to the death of premature babies. Moreover, RDS can be followed by respiratory complications, such as bronchopulmonary dysplasia (BPD), most commonly in those neonates who required ventilatory support and/or oxygen therapy for RDS treatment [4].

The pathophysiology of RDS has been correlated to lung immaturity and surfactant deficiency. Surfactant, a macro-aggregate composed of highly organized lipids and specific proteins, is produced by type 2 cells in the alveoli and placed in the air liquid interface. It mainly reduces surface tension and prevents alveolar collapse, particularly at end-expiration, so that adequate gas exchange is maintained throughout the ventilatory cycle [5].

Surfactant therapy has become the standard of care in management of preterm neonates with RDS since it was able to reduce mortality and the incidence of pulmonary air leaks such as pneumothorax by about 50% [6,7].

The current American [8] and European [3] approach for treatment of neonatal RDS recommends a policy of early initiation of non-invasive ventilation, like Continuous Positive Airway Pressure (CPAP), immediately after birth and early selective surfactant administration. This strong recommendation derives from different studies that demonstrated the role of CPAP as first-step stabilization of preterm neonates with RDS in combination with early rescue surfactant therapy [9,10]. A new technique to deliver surfactant intratracheally in spontaneously-breathing neonates by using a thin catheter in combination with CPAP has been described in the literature in the last years [11]. The development of this technique, most frequently called Less Invasive Surfactant Administration (LISA), has been based on the evidence from several studies that avoiding endotracheal MV and stabilizing very premature neonates on early CPAP in the delivery room may be one way of reducing BPD [12]. Indeed, even a short period of positive pressure ventilation could be harmful for the immature lung of

preterm neonates. Furthermore, LISA could allow administration of surfactant without the disadvantage of withholding non-invasive respiratory support [11].

A meta-analysis of seven randomized clinical trials (RCTs) comprising 3289 subjects confirmed that avoiding endotracheal MV reduces the combined outcome of death or BPD in preterm neonates <30 weeks' GA [12]. The early studies analyzed in the meta-analysis compared non-invasive respiratory support (e.g., CPAP) with standard intubation and rapid extubation after surfactant instillation, while more recent studies compared the LISA method with standard endotracheal intubation and surfactant administration. In spite of the differences of the study protocols and designs, the overall strategy of avoiding MV consistently led to a reduction in the incidence of death or BPD in all trials.

In Germany a first LISA technique with a soft, small diameter tube (gastric catheter) inserted through the nose into the pharynx with the use of Magill forceps has been described [13,14]. A second procedure, the Hobart method [15,16], has been proposed by an Australian group who uses a slightly stiffer vascular catheter, introduced through the mouth into the pharynx without the use of Magill forceps. In both procedures, the catheter is secured by the fingers of the neonatologist and surfactant slowly administered without withholding CPAP support. After surfactant instillation, the catheter is immediately removed. Maintaining the neonates on CPAP throughout the whole procedure seems helpful in reducing the incidence of desaturations.

The LISA method has only been evaluated in Investigator Initiated Trials (IITs) that showed promising results in terms of neonatal respiratory morbidity and seem to represent a significant improvement in the management of RDS [17,18].

The LISA method for porcine surfactant administration (poractant alfa, Curosurf[®], Chiesi Farmaceutici S.p.A.) has been approved and added to the current authorized methods/techniques by European Authorities and other countries outside of Europe; moreover, the specific thin catheter (CHF 6440), developed by Chiesi Farmaceutici S.p.A. (Parma, Italy) for poractant alfa delivery through LISA technique and used in the present study, has been approved (CE mark) in Europe as well as other countries.

This Phase IIIb explorative study is mainly aimed at investigating the safety and efficacy profiles of porcine surfactant (poractant alfa, Curosurf[®], Chiesi Farmaceutici S.p.A.) administered through LISA technique during a non-invasive respiratory support or conventional intubation with brief ventilation.

This trial will be conducted in compliance with the Declaration of Helsinki (1964 and amendments), the current ICH E6 Good Clinical Practices and all other applicable laws and regulations.

